2. INTRODUCTION

2.1. Background

A comprehensive review of pexidartinib (PLX3397) is contained in the Investigator's Brochure (IB). Investigators should review the latest IB prior to initiating this study. A brief review of pexidartinib is provided here.

2.1.1. Tenosynovial giant cell tumor

Tenosynovial giant cell tumor (TGCT) is a rare, nonmalignant neoplasm of the synovium, bursae, or tendon sheaths, generally affecting young adults (<40 years of age) of both sexes.² Symptoms initially may be minimal due to the slowly progressive nature of the disease. However, as the tumor mass grows and gradually expands within the intra- and extra-articular space, symptoms such as pain, stiffness, swelling, and reduced range of motion (ROM) of the affected joint can become severe and result in debilitating functional limitations. The diagnosis of TGCT is based on pathologic evaluation; however, features highly suggestive of the disease may be found on radiologic imaging (ie, magnetic resonance imaging [MRI]).

TGCT manifests as localized or diffuse disease. The localized type (known as giant cell tumor of the tendon sheath [GCT-TS]) constitutes 80% to 90% of TGCT cases and is usually a benign neoplasm that most commonly occurs in the digits. Localized TGCT can usually be treated effectively with surgery. The diffuse type (known as pigmented villonodular synovitis [PVNS]) constitutes 10% to 20% of cases and is a locally aggressive, nonmalignant neoplasm composed of synovial-like mononuclear cells, multinucleate giant cells, foam cells, siderophages, and inflammatory cells that may be intra- or extra-articular. Diffuse TGCT most commonly occurs in large joints, particularly the knee, ankle, and hip. In the United States (US), the annual incidence of new cases is estimated to be ~15,000 for localized TGCT and ~1500 for diffuse TGCT. A more recent survey in Denmark demonstrates an incidence of 4.4 per million population for localized TGCT and 1.2 per million population for diffuse TGCT, whereas a study in the Netherlands reports incidence rates (per million patient-years) of 34 for localized TGCT in the digits, 11 for localized disease in other extremities, and 5 for diffuse TGCT.

TGCT predominantly consists of mononuclear and multinucleated giant cells. Expansion of the tumor mass appears to be driven by the presence of abundant colony stimulating factor 1 (CSF-1), which is expressed by a subset of neoplastic cells within the tumor and is often associated with genetic translocations, eg, linking the collagen 6A3 gene on chromosomal locus 2q35 with the CSF-1 gene on chromosomal locus 1p13.⁷ The majority of cells in the tumor mass are non-neoplastic inflammatory cells that do not express CSF-1, but are attracted to the tumor site because of their expression of colony-stimulating factor 1 receptor (CSF1R).

The current standard of care for TGCT is as complete surgical resection of the tumor as possible to: (1) reduce pain, stiffness, and joint destruction caused by the disease process; (2) improve function; and (3) minimize the risk of recurrence. However, diffuse disease can be challenging to manage surgically. Patient outcome following surgery depends on multiple factors, including the location and extent of the disease. The overall recurrence rate in patients with focal disease is low, ranging from 0% to 6%²; however, in patients with diffuse forms of the disease,

recurrence is considerably more common, and is estimated to be in a range of 40%. Diffuse disease carries a risk of multiple recurrences, and affected patients often have more extensive involvement and a poorer likelihood of success with surgery. Surgical resection may involve the removal of major tendons or neurovascular structures, leading to significant postsurgical morbidity. Limb amputation may be required in severe, recurrent cases.²

No systemic antitumor agents have been approved for this indication in Japan. Anti-inflammatory and analgesic medications, including opioids, are commonly used as supportive therapy. In light of the severe morbidity that a patient can experience with this disease, a systemic therapy that provides a meaningful clinical benefit is highly needed.

2.1.2. Pexidartinib (PLX3397)

Pexidartinib is a small molecule tyrosine kinase inhibitor that targets CSF1R, KIT proto-oncogene receptor tyrosine kinase (KIT), and feline McDonough Sarcoma-like tyrosine kinase 3 (FLT3) harboring an internal tandem duplication (ITD) mutation. Pexidartinib inhibited the proliferation of cell lines that depend on CSF1R at concentrations below 1 µmol/L in vitro. Ligand-induced autophosphorylation of CSF1R is also inhibited by pexidartinib. Pexidartinib has been approved in the US for the treatment of TGCT associated with severe morbidity or functional limitations and not amenable to improvement with surgery.

2.2. Study Rationale

Clinical Experience

PLX108-10 (ENLIVEN Study): Pexidartinib or Placebo in Subjects with Tenosynovial Giant Cell Tumor

The ENLIVEN study was a 2-part, multicenter, phase 3 study in subjects with TGCT, for whom surgical resection would be associated with potentially worsening functional limitation or severe morbidity (locally advanced disease). In Part 1 (double-blind phase), eligible candidates were centrally randomized in a 1:1 ratio to receive either pexidartinib or placebo for 24 weeks (1000 mg/day [400 mg in the morning and 600 mg in the evening] or placebo for the first 2 weeks and 800 mg/day [400 mg twice a day {BID} or placebo for 22 weeks]. The subjects who completed Part 1 (ie, 24 weeks of dosing) were eligible to advance to Part 2, a long-term treatment phase where all subjects would receive open-label pexidartinib at a maximum starting dose of 800 mg/day.

The primary objective of this study was to compare the response rate of pexidartinib with that of placebo at Week 25. The secondary efficacy objectives were to evaluate 1) ROM at Week 25, 2) response based on tumor volume score (TVS) at Week 25, 3) patient-reported outcomes (PRO) at Week 25, and 4) duration of response.

Study PLX108-10 demonstrated a statistically significant improvement (p < 0.0001) in objective response rate (ORR) at Week 25 in the 61 patients randomized to pexidartinib (37.7% [95% confidence interval {CI}: 26.6%, 50.3%]) compared with placebo (0% [95% CI: 0, 6.1%]).

As of the data cut-off date of 31 Jan 2018, frequent treatment-emergent adverse events (TEAEs) (>20%) for subjects treated with pexidartinib in Part 1 were hair color changes (pexidartinib arm vs placebo arm: 67.2% vs 3.4%); fatigue (54.1% vs 35.6%); AST increased (39.3% vs 0%);

nausea (37.7% vs 40.7%); ALT increased (27.9% vs 1.7%); dysgeusia (24.6% vs 1.7%); arthralgia (23.0% vs 25.4%). Generally, the frequency of TEAEs in pexidartinib-treated subjects in Part 1 and Part 2 was only slightly greater than the frequency in Part 1 only, demonstrating that few new TEAEs occurred with long-term pexidartinib treatment. Most TEAEs occurred in the first 12 weeks of pexidartinib treatment. Please refer to the most recent IB for additional information.¹⁰

2.2.1. Study Rationale

The principal data supporting the efficacy of pexidartinib in TGCT have been indicated in the phase 3 study (Study PLX108-10 [ENLIVEN], N = 120) conducted in the US, Canada, European countries, and Australia. Pexidartinib was approved for adult patients with symptomatic TGCT associated with severe morbidity or functional limitations and not amenable to improvement with surgery by the US Food and Drug Administration (FDA) on 2 August 2019.

No systemic antitumor agents are approved for TGCT in Japan. A systemic therapy that provides a meaningful clinical benefit for TGCT patients is highly needed.

Similar safety, pharmacokinetics (PK), and efficacy as the ENLIVEN study can be expected in this Japan phase 2 study because there are no differences between the study populations of TGCT subjects in the ENLIVEN study and this Japanese phase 2 study in terms of extrinsic factors such as disease definition, diagnosis, medical practice and therapeutic approach. Regarding intrinsic ethnic factors, there is currently no evidence to indicate that the populations are not similar. Pexidartinib has the potential to offer a treatment option for TGCT patients in Japan.

2.3. Benefit and Risk Assessment

Pexidartinib has been approved in the US for the treatment of TGCT associated with severe morbidity or functional limitations and not amenable to improvement with surgery.

Safety data from nonclinical studies, clinical studies, and non-interventional studies have been reviewed. Hepatotoxicity is an important identified risk, and both embryo-fetal toxicity and fertility toxicity are considered an important potential risk with pexidartinib. In repeated dose toxicity studies in rats and dogs, male rats and dogs displayed testicular toxicity. Following a 16-week recovery period, testicular toxicity persisted in rats and partially recovered in dogs, but did not fully recover. Serious and prolonged hepatotoxicity with ductopenia and/or cholestasis has been observed in subjects treated with pexidartinib. Cases of cholestasis have been observed in the first 8 weeks and have generally resolved with treatment discontinuation, but in some cases have been severe, with a protracted course requiring liver dialysis and, in 1 case, transplantation. Hepatotoxicity may be fatal. One fatal case with ongoing cholestatic liver injury at the time of death has been reported. The mechanism of cholestatic hepatotoxicity is unknown, and its occurrence cannot be predicted. Protocol-defined dose reductions and discontinuations of pexidartinib, increased frequency of laboratory monitoring, and reporting of findings should be followed. In addition, rechallenge with pexidentinib should not be attempted. Risk minimization measures, such as frequent monitoring during the first 8 weeks of pexidartinib treatment related to managing these risks, should be conducted. Please refer to the most recent IB for additional information. 10

3. OBJECTIVES, OUTCOME MEASURES, AND ENDPOINTS

The objectives, definitions of associated endpoints as well as applicable outcome measures are described in Table 3.1. Further requirements for the endpoint analyses and censoring rules, where applicable, can be found in Section 9.5.1, Section 9.5.2, Section 9.5.3, and Section 9.5.4.

Table 3.1: Description of Objectives, Outcome Measures, and Endpoints

| Objectives | Outcome Measure | Endpoints | Category |
|---|---|--|----------|
| Primary | | | |
| Part 1: To evaluate the tolerability and PK of pexidartinib in Japanese | Title: DLT Description: Number of subjects with DLTs Time frame: C1D1 to C1D28 | Number of subjects with DLTs | Safety |
| subjects | Title: PK profile Description: Plasma concentrations and PK parameters of pexidartinib and ZAAD-1006a, the major metabolite of pexidartinib Time frame: C1D1-C1D2 and C1D15 (with intensive sampling) | Plasma concentrations and PK parameters of pexidartinib and ZAAD-1006a, the major metabolite of pexidartinib | PK |
| Part 2: To evaluate the efficacy of pexidartinib in Japanese subjects | Title: ORR based on RECIST 1.1 Description: ORR as assessed by centrally reviewed MRI scan based on RECIST 1.1 Time frame: Week 25 | ORR is defined as the proportion of subjects who achieved a CR or PR based on RECIST 1.1 by centrally reviewed MRI scan. No confirmation (ie, CR or PR at the subsequent MRI assessment) will be required for a CR or PR. | Efficacy |
| Secondary | | | |
| Part 2: To evaluate the efficacy of pexidartinib | Title: ORR based on TVS Description: ORR as assessed by centrally reviewed MRI scan based on TVS | ORR is defined as the proportion of subjects who achieved a CR or PR based on TVS by centrally reviewed MRI scan | Efficacy |
| | Time frame: Week 25 | | |
| | Title: ROM Description: Raw measurements of the affected joint with a goniometer Time frame: Week 25 | Mean change from baseline in ROM of the affected joint, relative to a reference standard for the same joint | Efficacy |
| | Title: PROMIS Physical Function Scale Description: PRO relevant to the assessment of lower and upper limb function Time frame: Week 25 | Mean change from baseline score in the PROMIS Physical Function Scale | Efficacy |
| | Title: BPI Worst Pain NRS | Proportion of responders based on the BPI Worst Pain NRS item and analgesic use by BPI-30 definition | Efficacy |

| Objectives | Outcome Measure | Endpoints | Category |
|--|--|---|----------|
| | Description: PRO relevant to the assessment of the "worst" pain in the last 24 hours | (ie, 30% or more improvement in average NRS) | |
| | Time frame: Week 25 | | |
| | Title: BOR based on RECIST 1.1 Description: BOR as assessed by centrally reviewed MRI scan based on RECIST 1.1 Time frame: At the time of the primary analysis: After all subjects have made the Week 25 visit or have discontinued from the study, whichever occurs first | BOR is defined as the proportion of subjects who achieved CR, PR, SD, PD, and NE recorded as the best response based on RECIST 1.1 by centrally reviewed MRI scan | Efficacy |
| | Title: BOR based on TVS Description: BOR as assessed by centrally reviewed MRI scan based on TVS Time frame: At the time of the primary analysis | BOR is defined as the proportion of subjects who achieved CR, PR, SD, PD, and NE recorded as the best response based on TVS by centrally reviewed MRI scan | Efficacy |
| | Title: DoR based on RECIST 1.1 Description: DoR as assessed by centrally reviewed MRI scan based on RECIST 1.1 Time frame: At the time of the primary analysis | DoR is defined as the time from the date of the first recorded response to the first date of documented disease progression | Efficacy |
| | Title: DoR based on TVS Description: DoR as assessed by centrally reviewed MRI scan based on TVS Time frame: At the time of the primary analysis | DoR is defined as the time from the date of the first recorded response to the first date of documented disease progression | Efficacy |
| Part 1, Part 2: To assess the safety of pexidartinib | Title: TEAEs and other safety parameters during the study* Description: Descriptive statistics of safety endpoints Time frame: Continuous monitoring and reported at the time of each data cut-off *Though this is a secondary objective, this is a primary outcome measure | Safety evaluation include the following, but is not limited to: TEAEs, drug induced hepatotoxicity, laboratory tests, vital signs, and ECGs | Safety |
| Part 1, Part 2: To evaluate the PK properties of pexidartinib | Title: PK profile Description: Plasma concentrations and PK parameters of pexidartinib and ZAAD-1006a | Plasma concentrations and PK parameters of pexidartinib and ZAAD-1006a, the major metabolite of pexidartinib | PK |

| Objectives | Outcome Measure | Endpoints | Category |
|---|--|---|----------|
| | Time frame: Part 1; C2D1, C3D1, and C5D1 (with sparse sampling), Part 2; C1D1-C1D2 and C1D15 (with intensive sampling) and C2D1, C3D1, C5D1 (with sparse sampling) | | |
| Exploratory | | | |
| Part 2: To evaluate the efficacy of pexidartinib | Title: ORR based on RECIST 1.1 Description: ORR as assessed by locally reviewed MRI scan based on RECIST 1.1 Time frame: Week 25 | Proportion of subjects who achieve a CR or PR of pexidartinib based on RECIST 1.1 at Week 25 by locally reviewed MRI scan | Efficacy |
| | Title: Tumor response based on modified RECIST 1.1-sum of the short-axis dimension (SSD) Description: Tumor response as assessed by centrally reviewed MRI scan based on modified RECIST 1.1-SSD Time frame: Week 25 | Proportion of subjects who achieve a CR or PR of pexidartinib based on modified RECIST 1.1-SSD at Week 25 by centrally reviewed MRI scan | Efficacy |
| | Title: EQ-5D-5L Description: Mean change from baseline score in the EQ-5D-5L at Week 25 Time frame: Week 25 | Mean change from baseline score in the EQ-5D-5L at Week 25 | Efficacy |
| | Title: BOR based on RECIST 1.1 Description: BOR as assessed by locally reviewed MRI scan based on RECIST 1.1 Time frame: At the time of the primary analysis | BOR is defined as the proportion of subjects who achieved CR, PR, SD, PD, and NE recorded as the best response based on RECIST 1.1 by locally reviewed MRI scan | Efficacy |
| | Title: DoR based on RECIST 1.1 Description: DoR as assessed by locally reviewed MRI scan based on RECIST 1.1 Time frame: At the time of the | DoR is defined as the time from the date of the first recorded response to the first date of documented disease progression | Efficacy |
| | primary analysis Title: DoR based on modified RECIST 1.1-SSD Description: DoR as assessed by centrally reviewed MRI scan based on modified RECIST 1.1-SSD Time frame: At the time of the primary analysis | DoR is defined as the time from the date of the first recorded response to the first date of documented disease progression | Efficacy |

| Objectives | Outcome Measure | Endpoints | Category |
|---|--|--|--------------------|
| | Title: Photographic documentation Description: Photographs of tumor appearance Time frame: At the time of the primary analysis | Change in appearance of tumor by photographs from baseline to the time of analysis | Efficacy |
| | Title: Surgical Assessment Questionnaire Description: Assessment of the surgical status Time frame: At the time of the primary analysis | Results of the Surgical Assessment Questionnaire | Efficacy |
| | Title: Long-term subject status Description: Assessment of subject status during the follow-up period by telephone contact Time frame: At the time of the primary analysis | Results of the LTFU questionnaire after the end of study or early termination visit | Efficacy |
| Part 1: To evaluate the efficacy of pexidartinib | The outcome measures planned for assessing the efficacy of the primary objectives, the secondary objectives, and the exploratory objectives | | Efficacy |
| To characterize associated biomarkers in peripheral blood and tumor tissue that may predict the efficacy and safety of pexidartinib | Not applicable | Relationship between clinical outcome and Plasma CSF-1 and IL-34 concentrations (ELISA) CSF1R gene mutations (NGS) Profile of drug-metabolizing enzyme and transporter gene mutations (PharmacoScan assay) Profile of tumor-infiltrating immune cells (immunohistochemistry) Profile of immune cells in peripheral blood (flow cytometry) CSF-1 rearrangements (FISH, DNA sequencing) Subject's samples will be banked for future biomarker analyses, which may include comprehensive gene mutation and gene expression profiling with NGS and RNA-sequencing | Biomarkers/ PGx |

BOR = best overall response; BPI = brief pain inventory; C = cycle; CR = complete response; D = Day; DLT = dose-limiting toxicity; DoR = duration of response; ECG = electrocardiogram; ELISA = enzyme-linked immunosorbent assay; EQ-5D-5L = The five-level version of EuroQol five-dimensional questionnaire; FISH = fluorescence in situ hybridization; LTFU = long-term follow-up; MRI = magnetic resonance imaging; NGS = next

generation sequencing; NE = not evaluable; NRS = numeric rating scale; ORR = objective response rate; PD = progressive disease; PGx = pharmacogenomics; PK= pharmacokinetics; PR = partial response; PRO = patient-reported outcomes; PROMIS = patient-reported outcomes measurement information system; RECIST= response evaluation criteria in solid tumors; ROM = range of motion; SD = stable disease; SSD = sum of the short-axis dimension; TEAE = treatment-emergent adverse event; TVS = tumor volume score

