AE = adverse event; ALT = alanine aminotransferase; AMA = Anti-mitochondrial antibody; AST = aspartate aminotransferase; BPI = brief pain inventory; C = cycle; D/d = Day; CQ = chloroquine; ECG = electrocardiogram; End St./Ear. Term. = end of study/early termination; EQ-5D-5L = The five-level version of EuroQol five-dimensional questionnaire; FSH = follicle-stimulating hormone; HCQ = hydroxychloroquine; incl. = including; LTFU = long-term follow-up; MRI = magnetic resonance imaging; NRS = numeric rating scale; Pdy = pharmacodynamic(s); PGx = pharmacogenomic(s); PK = pharmacokinetic(s); PROMIS = patient-reported outcomes measurement information system; Pt = patient; SARS-CoV-2 = severe acute respiratory syndrome coronavirus 2; TGCT = tenosynovial giant cell tumor; Tx = treatment.

- a. The procedures are performed on C10D1 and every 12 weeks thereafter (eg, C13, C16, C19).
- b. Patients who exit the study with radiological disease progression will undergo their last study evaluation at 28 ± 7 days after their last dose of the study drug and before any new TGCT therapy, including surgery, whichever occurs first. Any planned new TGCT therapy, including the type of surgical procedure, will be recorded. Patients who withdraw from the study with radiological progression do not undergo an End of Study/Early Termination MRI.
- c. Patients who end their study participation with no radiological disease progression will undergo post-treatment procedures at 28 ± 7 days after their last dose of the study drug or before any new TGCT therapy, including surgery, whichever occurs first. The latter MRI need not be performed if new TGCT therapy starts within 4 weeks of the Post-treatment visit. Before or at the End-of-Study/Early Termination visit, plans for any new TGCT therapy will be obtained.
- d. Every 6 months after the End of Study/Early Termination.
- e. Vital signs should be measured before any invasive procedures are carried out on the same day.
- In the event of early withdrawal, a physical examination is performed at the Post-treatment visit.
- g. Patients receiving concomitant warfarin should have their anti-coagulation status carefully monitored for any necessary dose adjustments.

- h. Women who are not using hormonal contraception must be tested for levels of FSH, luteinizing hormone (LH), progesterone, and estradiol. Hormone testing will not be required for women who have either had an oophorectomy or are post-menopausal.

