- i. A washout period of no less than 14 days is required before restarting pexidartinib.
- j. Optional.
- k. A serum sample should be collected for AMA when severe hepatotoxicity is observed.
- 1. Before any invasive procedures on the same day, PROMIS Physical Function Scale, BPI Worst Pain NRS, and EQ-5D-5L are to be recorded.
- m. Subjects will complete the BPI Worst Pain NRS item for seven consecutive days prior to the indicated study visits, as well as on the day of the study visit. In addition, subjects will complete the BPI Worst Pain NRS item on an outpatient basis prior to the indicated study visits.
- n. If surgical resection of the tumor is performed within the designated time period (28 days for Post-Tx and 12 weeks for End of Study/Early Termination) after the last dose of the study drug, details of the surgery and its outcome should be obtained.
- *: Not be performed from Protocol Version 4.0 onwards.
- **: From Protocol Version 4.0 onwards, only local review will be performed, and central review will not be performed.
- ***: MRI are performed every 24 weeks from Protocol Version 4.0 onwards.

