During the study, if indicated, Investigators should request confirmation of radiological disease progression by central read. Otherwise, central reading of MRI scans may be performed during or after the subject has completed the study. While progression status will be assessed only by local read from Protocol Version 4.0 onwards. The details for MRI scan read are outlined in the MRI Procedure Manual.

Subjects who terminate the study because of radiological disease progression will NOT have a follow-up MRI at their post-treatment visit.

Tumor Volume Score

TVS is a semi-quantitative MRI scoring system that describes tumor mass and is an extension of the 4-point synovitis scale of the well-established and widely used multi-feature score (Rheumatoid Arthritis MRI Score), originally developed for rheumatoid arthritis ¹³ and whole-organ MRI score (WORMS), originally developed for osteoarthritis. ¹⁴ The extended scale, the TVS, will be based on 10% increments of the estimated volume of the maximally distended synovial cavity or tendon sheath involved. Thus, a tumor that is equal in volume to that of a maximally distended synovial cavity or tendon sheath will be scored 10, whereas a tumor that is 70% of that volume will be scored 7, a tumor that is twice the volume of the maximally distended synovial cavity or tendon sheath will be scored 20, and so on. A score of "0" means no evidence of tumor.

Individual subject outcomes by TVS will be classified according to the following criteria inspired by RECIST 1.1:

- CR: Lesion completely gone.
- PR: >50% decrease in volume score relative to baseline.
- PD: ≥30% increase in volume relative to lowest score during the study whether at baseline or some other visit. In the case of limited residual disease, the increase in tumor volume must also be unequivocally larger.
- SD: Does not meet any of the prior criteria based on score during study.

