9. STATISTICAL CONSIDERATIONS

9.1. General Statistical Considerations

The data cutoff for the primary analysis will occur after all subjects have either discontinued the study or completed at least Week 25 assessments. The final analysis of the study will occur after all subjects have discontinued the study. Data collected beyond the primary analysis cut-off time point will be presented as appropriate in a CSR addendum.

The data cutoff for safety and PK analysis in Part 1 will occur after all subjects have received pexidartinib and have either completed the minimum safety evaluation requirements over the DLT evaluation period (28 days) or have experienced a DLT during the DLT evaluation period.

Data analysis will also be conducted separately by Part 1 and Part 2. The pooled analysis may be planned in the Statistical Analysis Plan (SAP).

Continuous variables will be summarized by the number of observations, mean, standard deviation, median, 25th and 75th percentile, and minimum and maximum values. Categorical variables will be summarized using frequency counts and percentages.

Assessments of change from baseline to post-treatment or the ratio of post-treatment to baseline will include only those subjects with both baseline and post-treatment measurements. The last non-missing value of a variable taken before the first dose of the study drug will be used as the baseline value, unless otherwise specified. In general, missing or dropout data will not be imputed for the purpose of data analysis, unless otherwise specified.

For the primary and secondary efficacy endpoints, with the exception of duration of response, the point estimate and accompanying 95% CI will be computed. For duration of response, Kaplan-Meier product limit methodology will be utilized to provide estimates, including those for the median and 25th and 75th percentiles.

No formal interim analysis is planned in Part 1 or Part 2.

For all analysis, the Part 1 data at the end of Part 1 will be used.

The all analysis including the efficacy analysis of the subjects in Part 1 was originally planned to be performed at the end of Part 2. However, the sponsor decided not to proceed with Part 2. Depending on this decision, the Part 1 data will be analyzed at the end of Part 1, and the efficacy analysis will be performed as the exploratory analysis.

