9.5.1.3. Exploratory Analyses

The exploratory efficacy endpoints will be provided in Part 2:

- Proportion of subjects who achieve a CR or PR (ORR) at Week 25 based on RECIST 1.1 by locally reviewed MRI scan.
- Proportion of subjects who achieve a CR or PR (ORR) at Week 25 based on modified RECIST 1.1- sum of the short-axis dimension (SSD) by centrally reviewed MRI scan.
- Mean change from baseline score in the EQ-5D-5L at Week 25
- BOR based on RECIST 1.1 by locally reviewed MRI scan
- DoR based on RECIST 1.1 by locally reviewed MRI scan
- DoR based on modified RECIST 1.1-SSD by centrally reviewed MRI scan

A brief description of each analysis is provided below:

- An estimate of the proportion responders based on (i) RECIST 1.1 by local and (ii) modified RECIST 1.1-SSD by central evaluation and the two-sided 95% CI based on the Clopper-Pearson method will be calculated. Subjects who do not provide data for the endpoint will be considered to be non-responders.
- Change from baseline in EQ-5D-5L will also be summarized with point estimates and 95% CIs.
- The percentage and 95% CI will be provided for BOR in the order of CR, PR, SD, PD, and NE.
- DoR will also be analyzed as a secondary endpoint and will be summarized for responders based on (i) RECIST 1.1 by local and (ii) modified RECIST 1.1-SSD by central evaluation. For subjects who do not have radiological progression, the

duration of response will be censored. Subjects not known to have experienced an event at the time of the data cut-off will be censored at the date of the last tumor assessment before the cut-off date. The SAP includes additional censoring rules. The Kaplan-Meier product limit method will be used to compute the estimate and 95% CI of the median and the 25th and 75th percentiles.

Exploratory efficacy analyses will also be performed in Part 1.

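### Version 4.0 doubles the MRI interval after Cycle 7 from 12 to 24 weeks, which by itself lengthens recorded local-read duration of response for responders who progress after the change

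*Combined protocol and SAP*

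**What the plan says.** Table 1.3 (Section 1.3) governs the period after Cycle 7 Day 1. Its footnote a reads: "The procedures are performed on C10D1 and every 12 weeks thereafter (eg, C13, C16, C19". The triple-asterisk footnote, attached to MRI alone, then says: "MRI are performed every 24 weeks from Protocol Version 4.0 onwards".

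On reading, Section 8.3 says: "While progression status will be assessed only by local read from Protocol Version 4.0 onwards". Central reading covers scans up to Version 3.0 only.

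Table 3.1, exploratory block, local read: "DoR is defined as the time from the date of the first recorded response to the first date of documented disease progression". Section 9.5.1.3 gives the estimator: "The Kaplan-Meier product limit method will be used to compute the estimate and 95% CI of the median and the 25th and 75th percentiles". It says that subjects without a known event "will be censored at the date of the last tumor assessment before the cut-off date. The SAP includes additional censoring rules". No separate SAP text accompanies the protocol, so those further rules cannot be checked.

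The endpoint is live for the nine enrolled subjects. Section 9.5.1.3 adds: "Exploratory efficacy analyses will also be performed in Part 1". Table 3.1 and Section 9.5.1 likewise carry the efficacy measures into Part 1 as exploratory. On timing, Table 3.1 places response duration at the primary analysis, which Section 9.1 sets once all subjects have reached Week 25 or left the study. Section 9.1 also says: "For all analysis, the Part 1 data at the end of Part 1 will be used". It does not attach a date to the end of Part 1.

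**The concern.** Apart from unscheduled imaging, radiological progression can be documented only at a planned scan. If the gap between scans doubles, a progression that would have been seen at the skipped scan is dated 12 weeks later, and no progression is dated earlier. Events before and after Version 4.0 then enter one Kaplan-Meier curve with different detection delays, and the output gives no sign of it. Local-read duration is the version affected, because central-read durations (RECIST 1.1, tumor volume score, modified RECIST) stop gathering new scans at Version 4.0.

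At stake is the description of durability. With so few responders, one event dated 12 weeks late can shift a reported quartile or median, and a reader would take the gain for a drug effect.

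**Working it through.** The documents give no numerical duration of response, so there is no figure to reproduce.

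**Inputs from the documents.** Scan interval L = 12 weeks before and 24 weeks from Version 4.0 (Table 1.3). Version 4.0 is dated 27 Aug 2024 (Document History). Dosing may continue until February 2026 (Section 4.1.4). Nine subjects were enrolled (Section 4.1.1).

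**Assumptions.** Durations are exponential with true median 26 to 208 weeks, so λ = ln 2 / median. Progression is found at the next scheduled scan. Visit windows are ignored. The version date stands for the date of the switch.

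**Step 1: mean detection delay.** For interval L it is L / (1 − exp(−λL)) − 1/λ, which tends to L/2. For a true median of 52 weeks, λ = 0.01333 and 1/λ = 75.02. At L = 12 the delay is 12/0.1478 − 75.02 = 6.16. At L = 24 it is 24/0.2738 − 75.02 = 12.64.

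| True median (weeks) | Delay, 12-week scans | Delay, 24-week scans | Added |
|---|---|---|---|
| 26 | 6.32 | 13.27 | 6.95 |
| 52 | 6.16 | 12.64 | 6.48 |
| 104 | 6.08 | 12.32 | 6.24 |
| 208 | 6.04 | 12.16 | 6.12 |

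**Step 2: what an individual sees.** The gain is 12 weeks if progression falls in the first half of a 24-week gap and zero otherwise. The first-half probability is 1 / (1 + exp(−12λ)). For a median of 52 weeks this is 1/1.852 = 0.540, and 12 × 0.540 = 6.48, which agrees with Step 1. In simulations with medians of 52 to 208 weeks and the switch at Week 24, 48 or 96 of response, 51% to 54% of post-switch progressions are recorded 12 weeks later and the rest are unchanged. Averaged over all events, including those before the switch, recorded duration rises by 1.3 to 4.4 weeks.

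**Step 3: the Kaplan-Meier median.** In a large sample it is the first scan at or after the true median, so it depends on scan phase.
- Scans every 12 weeks: true medians of 52, 78 and 104 are recorded as 60, 84 and 108.
- Switch at Week 24 or 48: later scans fall at 72, 96 and 120, so the same medians move one step, follow-up permitting. True medians of 65, 90 and 115 are recorded as 72, 96 and 120 under either schedule and do not move.
- Switch at Week 36: scans fall at 60, 84 and 108, so true medians of 52, 78 and 104 do not move.
- With about 78 weeks of follow-up after the switch, the simulated median is not reached in several scenarios (for example, true median 104 with the switch at Week 24, or true median 208 with any of the three switch times).

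**Step 4: exposure.** From 27 Aug 2024 to 28 Feb 2026 is 78.6 weeks. 78.6/12 = 6.5, so six scans; 78.6/24 = 3.3, so three. If the last subject started by 30 June 2024 (assumed), 24 weeks of dosing end on 15 Dec 2024, about 16 weeks after Version 4.0. That is less than one 24-week gap, so a Week 25 cut-off would include few scans on the new spacing.

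**Step 5: number of responders.** At the 37.7% response rate assumed for Part 2 (Section 9.3), 9 × 0.377 = 3.4, so about 3 to 4.

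**The case against.** The strongest reply is about reach. Table 3.1 times response duration at the primary analysis, when few 24-week scans exist, and Section 9.1 sends later data to a report addendum as appropriate. This stands if that cut-off is used. But Section 9.1 also names the end of Part 1 and plans a final analysis after all subjects have left the study, so a later cut-off is open.

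Second, only responders still progression-free at Version 4.0 are touched; percentiles set by earlier events do not move. Unscheduled imaging for clinical worsening, and post-treatment or end-of-study MRI off the 24-week grid, would shorten the delay. A response first seen on a 24-week scan would start the clock late and partly offset it. All of this stands and limits the size.

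Third, a reader might infer that the reported median is inflated by a full 12 weeks. The documents do not support that: Step 3 shows a shift, no shift or no estimate, according to scan phase. Nor could a 120-week median be observed if the switch came at Week 24 of response. It needs a scan 96 weeks after the switch, against about 79 weeks of remaining dosing, and even a final MRI 12 weeks (+7 days) after the last dose reaches only about 92.

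Fourth, the SAP may handle this in its additional censoring rules. That cannot be excluded, but the rule shown governs subjects without an event and leaves the event date alone.

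Fifth, an interval-censored estimate on 3 to 4 responders is barely informative, and dating progression at the last clear scan creates the opposite bias, which also grows with the gap. Both are fair; they argue for showing bounds, not for replacing the main analysis.

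**Conclusion.** The point holds in limited form. The plan mixes two detection intervals in one local-read curve, and nothing in the text supplied adjusts for it. Each progression found on a scheduled scan after Version 4.0 gains about 6 weeks on average, between 0 and 12, under exponential durations and ignoring visit windows. The direction of this effect on the event date follows from the definition and needs no distributional assumption; the average does.

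The consequence is modest: an exploratory, single-arm, untested summary in at most nine subjects. It is negligible at a Week 25 cut-off and worth correcting for an analysis near February 2026. A general claim that the median and quartiles are biased upward would go too far. The central-read durations are not lengthened this way.

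**What to change.** In Section 9.5.1.3, or in the SAP before database lock:
- Keep the current Kaplan-Meier as the main exploratory analysis of local-read duration.
- List, for each local-read responder, the last progression-free MRI date and the first MRI date showing progression.
- Add one sensitivity Kaplan-Meier with progression dated at the last progression-free scan. Present it with the main curve as lower and upper bounds for the dating of progression. An interval-censored estimate is optional.
- Footnote the output with the change in MRI interval at Version 4.0.

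No visit or scan changes, and the dates come from scans the trial already performs. The cost is one extra output, a wider range and a less favourable lower bound.
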